13. Blood chemistry and coagulation (local lab): Alkaline phosphatase (AP), total bilirubin, aspartate transaminase (AST/ SGOT), alanine transaminase (ALT/ SGPT), lactate dehydrogenase (LDH), and uric acid, C-reactive protein (CRP), sodium, potassium, calcium, blood urea nitrogen, creatinine, glucose: at baseline and during vaccination phase, thereafter at each visit using individual institutional guidelines and the best clinical judgment of the responsible physician, which can involve more frequent testing. Prothrombin time, aPTT, and fibrinogen will be measured at baseline and at investigator's discretion during treatment.
14. Immunoglobulin/immunophenotype: Assessment of IgA, IgG and IgM; lymphocyte subsets: T (CD4⁺ and CD8⁺) as well as B and NK cells.
15. Urine analysis (local lab): pH, glucose, proteins (qualitative, dipstick accepted): at baseline and at investigator's discretion during treatment
16. HBV, HCV and HIV-1: at baseline and thereafter at investigator's discretion
17. Pregnancy testing: For all FCBP, pregnancy testing has to be performed at the screening visit. Negative results must be available prior to vaccination.
18. SARS-CoV-2 testing: Volunteer must be tested for prior or current SARS-CoV-2 infection. Patients should be tested by serological test and throat/nose swab. If screening takes more than 48 hours, throat/nose swab for SARS-CoV-2 infection must be repeated. The vaccine can only be applied if a negative SARS-CoV-2 PCR test is available on the day of vaccination not older than 48 hours. If patients develop SARS-CoV-2 typical symptoms until vaccination, testing should be repeated.
19. Vaccine CoVac-1: Peptide vaccination should be started as soon as possible after the screening visit. Peptide vaccination will be performed once.
20. T-cell response: 60 ml of heparin blood for immunomonitoring and analysis of peptide specific T-cell response will be analyzed by the [name] lab, KKE Translational Immunologie at the Department of Immunology, Tuebingen (central laboratory). Blood will be taken before peptide vaccination on V1, and during vaccination phase and follow-up at each visit.
21. Serological response: 10 ml of serum for analysis of serological response will be analysed by the Immunopathological Laboratory, University Hospital Tuebingen (central laboratory). Blood will be taken before peptide vaccination on V1, and during vaccination phase and follow-up at each visit.

1. Introduction

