2.1.1. Primary Endpoint

The nature, frequency, and severity of AEs and/or SAEs associated with administration of CoVac-1:

- Solicited: ADRs/AEs occurring from the time of each injection throughout 28 days following the procedure, facilitated by use of a volunteer diary
- Unsolicited: AEs from the time of injection throughout 56 days following injection
- SAEs from the time of injection until the final study visit for each subject
- Incidence of AESIs until the final study visit for each subject

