- Medical history, anamnestic evaluation of SARS-CoV-2 specific symptoms
- T-cell response, approximately 60 ml blood
- Serological response, approximately 15 ml blood

6.2.7. *Volunteer's diary/card*

Each patient included in the P-pVac-SARS-CoV-2 study will receive a volunteer's card, which states that he/she is participating in the study (Appendix 13.4). This will also include a 24h emergency contact number. Furthermore, each patient will be provided with a volunteer's diary to note their symptoms daily (Appendix 13.3)

6.2.8. *Unscheduled Visit*

Subjects may contact the investigator at any time for an unscheduled phone or on-site visit should they experience clinical symptoms or signs following injection. At all unscheduled visits, the following minimum assessment will be performed: Questions concerning the history of the present illness as well as the subject's general health and lifestyle. Findings resulting in (S)AEs

Protocol		
Protocol code and Short Title:	P-pVAC-SARS-CoV-2	Date/Version:08.03.2021/V1.4

will be documented and reported as indicated. All other symptoms/signs will be reported on the next scheduled visit on eCRF.

Upon occurrence of symptoms characteristic of SARS-CoV-2 (i. e. cough, fever (cut-off $>39^{\circ}\text{C}$), loss of taste and smell, limb pain) at any time until day 56, subjects are supposed to get in touch with the investigator. Investigator will initiate SARS-CoV-2 testing for the volunteer (nose or mouth swab followed by PCR per institutional guidelines). If the test is positive, patients should be treated per investigators discretion. Positive results must be recorded as an AESI (section 9.1.4). Negative results will be followed by a second testing $\geq 24\text{h}$ later. Only upon the second negative test, patients are considered negative, all others must be reported as positive.

If participants are positively tested for SARS-CoV-2, all accompanying symptoms and treatments (e.g. hospitalisation, ICU) are recorded

Medically attended AEs and all SAEs will be recorded, and concomitant medication or vaccination will be noted. After identifying the history of the present illness and performing corresponding exams or laboratory tests, the investigator will decide on the best course of treatment according to standard medical practice.

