The frequency and functionality of peptide-specific CD8⁺ T cells is analyzed by intracellular IFN- γ or TNF staining as described previously.^{114 116} PBMCs are pulsed with individual peptide and incubated in the presence of Brefeldin A and GolgiStop. Cells are labeled using

Protocol		
Protocol code and Short Title:	P-pVAC-SARS-CoV-2	Date/Version:08.03.2021/V1.4

Cytofix/Cytoperm, CD8, CD4, TNF and IFN- γ coupled to fluorochromes. Samples are evaluated on a FACS analyzer.

Enzyme-linked immunosorbent assay (ELISA)

To identify SARS-CoV-2 antibody responses induced by the vaccine, ELISA assays will be performed using serum samples (15 ml serum tube) obtained at the time points described in Table 1. Specific antibodies against the seven SARS-CoV-2 T-cell epitopes will be assessed by ELISA assay at the Department of Immunology, Tübingen. To differ between vaccine induced antibody response additional standard Elecsys® Anti-SARS-CoV-2 assay supplied by F. Hoffmann-La Roche AG, Basel, Switzerland or ADVIA Centaur SARS-CoV-2 Total (COV2T) (Siemens Healthcare Diagnostics GmbH) will be performed at central laboratory of the University Hospital Tuebingen.

Occurrence or relevant (≥ 2 -fold) increase of SARS-CoV-2 specific IgG antibodies compared to baseline are considered as positive.

In the unlikely event of antibody induction by the CoVaC-1 vaccine, neutralization capacity of antibodies will be assessed by SARS-CoV-2 Pseudovirus Neutralization Assay (CD, Creative Diagnostics®)

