9.1.4. AESI (adverse events of special interest)

An adverse event of special interest (AESI), serious or non-serious, is one of scientific and medical concern specific to the sponsor's product, for which ongoing monitoring and rapid communication (≤ 48 hours) by the investigator to the sponsor can be appropriate. Such an event might warrant further investigation in order to characterize and understand it. Depending on the nature of the event, rapid communication by the trial sponsor to other parties (e.g. regulators) might also be warranted (adapted from CIOMS 2005).

In case of the CoVac-1 vaccine in this study, AESIs include proven SARS-CoV-2 infection and potential immune mediated diseases (pIMDs, see Appendix 14.6)¹¹⁷. Instructions for management are provided in section 6.3.

With regard to trial schedule and AESI occurrence, AESIs constitute:

- Novel proven (PCR-based) SARS-CoV-2 infection accompanied by symptoms
- Novel proven (PCR-based) SARS-CoV-2 positivity without symptoms
- Novel potential immune mediated diseases (pIMD) according the listed diseases in Appendix 14.6
- Formation of granuloma at the injection site

AESIs are always to be addressed as part of the patient safety report to the DSMB (section 1.4), also non-occurrence will be mentioned. Depending on the decision of DSMB, the vaccination of further volunteers will be permanently stopped.

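### The SARS-CoV-2 component of AESI incidence may be misclassified in either direction, because the testing rule matches neither the PCR-proven definition nor the six-month window

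*Supplement*

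**What the plan says.** All references are to protocol V1.4.

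- **Endpoint (2.1.1).** The primary endpoint includes "Incidence of AESIs until the final study visit for each subject". The final visit is V7, six months after vaccination (Table 1, footnote 2).
- **Definition (9.1.4).** The AESI list names "Novel proven (PCR-based) SARS-CoV-2 infection accompanied by symptoms" and also "Novel proven (PCR-based) SARS-CoV-2 positivity without symptoms". Immune-mediated disease and injection-site granuloma are on the same list.
- **Testing rule (6.2.8).** If listed symptoms occur "at any time until day 56, subjects are supposed to get in touch with the investigator", who then orders a PCR. A negative result is to be followed by a second test at least 24 hours later. The rule ends: "Only upon the second negative test, patients are considered negative, all others must be reported as positive".
- **Scheduled testing (Table 1).** SARS-CoV-2 testing is marked at screening only. Footnote 18 ties it to eligibility: "The vaccine can only be applied if a negative SARS-CoV-2 PCR test is available on the day of vaccination not older than 48 hours".
- **After day 56.** Section 6.2.6 lists, for V6 and V7, "Medical history, anamnestic evaluation of SARS-CoV-2 specific symptoms" and blood for T-cell and serological assays, with no PCR and no adverse-event assessment. Table 1 does mark adverse-event assessment at V6-7, while 9.2 ends adverse-event collection at Visit 5.
- **Serology.** Serum is drawn at V1 and every later visit (Table 1, footnote 21). Section 6.3.2 adds commercial anti-SARS-CoV-2 assays to the vaccine-peptide ELISA, introduced by "To differ between vaccine induced antibody response additional standard". No section says how a positive result bears on the AESI count.

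**The concern.** Two things do not fit together. First, 9.1.4 requires proof by PCR, while 6.2.8 turns an absent second swab into a reported case. In that situation a site cannot follow both sections, and a missing result becomes an event. Second, the PCR the protocol orders does not reach what the endpoint counts. Asymptomatic positivity is a named AESI, but no PCR is ordered after vaccination without symptoms. AESIs count to month six, but the symptom-to-PCR instruction stops at day 56.

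Section 1.2.1 gives PCR-proven AESI reporting as the mitigation for possible immune pathology in infected vaccinees. Section 9.1.4 sends AESIs to the safety board, whose decision can permanently stop vaccination. With 36 volunteers, a single misclassified case is visible in the SARS-CoV-2 rate.

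**Working it through.** **The plan's own figures.** No figure is given for AESI incidence. The only design calculation (8.1.1) concerns serious adverse events, and it reproduces:
- power: 1 − 0.95^33 = 0.816
- significance level: 1 − 0.9999^33 = 0.0033, stated as 0.003
- total: 33/(1 − 0.075) = 35.7, rounded up to 36

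No input to it depends on how AESIs are ascertained.

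**Upward error.** Section 6.2.8 allows four paths:

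| First swab | Second swab | 6.2.8 reports | PCR proof (9.1.4) |
|---|---|---|---|
| positive | – | positive | yes |
| negative | positive | positive | yes |
| negative | negative | negative | no |
| negative | missing | positive | no |

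Only the last row conflicts. Each such case moves the SARS-CoV-2 AESI rate by 1/36 = 2.8 points overall, 1/12 = 8.3 points in Part I, or 1/24 = 4.2 points in Part II.

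The expected number is 36 × s × m. Here s is the share of volunteers who are uninfected, have trigger symptoms and test negative first; m is the share of those who miss the repeat. Neither is in the documents. Assuming s of 5–30% and m of 0–20%, the range runs from 0 to 36 × 0.30 × 0.20 = 2.2. It is exactly 0 if every second swab is done.

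**Window.** Taking six months as 183 days, the symptom trigger covers 56/183 = 0.306 of the endpoint window and leaves 127/183 = 0.694. With 180 days the covered share is 56/180 = 0.311. No assumption about infection rates is needed.

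**Share of infections reached by the symptom-triggered route.** This step rests on outside assumptions: constant incidence over six months and an asymptomatic fraction y of 20–50%.

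Captured share c = (56/183) × (1 − y):
- y = 20%: 0.245
- y = 40%: 0.184
- y = 50%: 0.153

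Infections among 36 volunteers outside this route are 36 × a × (1 − c). For an assumed six-month attack rate a of 1–10%, that runs from 36 × 0.01 × 0.755 = 0.27 to 36 × 0.10 × 0.847 = 3.05. These figures give no credit to history, unscheduled contact, outside PCR or serology. They describe one route, not the trial's total capture.

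**Any-AESI incidence.** Granuloma is itself an AESI and occurred in 12 of 12 Part I volunteers (5.7.2.1). A missed or false SARS-CoV-2 case would barely move a pooled AESI rate.

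**The case against.** The case against a larger finding is strong in several respects.

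- **Detection.** A reader might infer that asymptomatic or late infection cannot be detected at all. The documents do not support that. V6 and V7 take a symptom history, Table 1 marks adverse-event assessment there, and volunteers may contact the investigator at any time. The definition in 9.1.4 needs a PCR but not one ordered by the protocol, so an outside result could count. What stands is narrower: no PCR is mandated for these cases, and serological evidence has no stated route into the count.
- **Certainty of error.** A reader might infer that the rate is bound to be wrong. It is not. The repeat swab is required, so upward error needs a protocol deviation. Downward error needs an infection that no other route brings to light. Reporting an unresolved case as positive is also a defensible caution for rapid safety reporting. It is less suitable for a tabulated incidence of proven infection.
- **T-cell results.** A reader might infer that undetected infections will be scored as vaccine responders. Section 6.3.2 adds epitopes outside the vaccine to separate natural from vaccine-induced responses. The cellular conversion rate is calculated only at V2 to V5, and Part I already stood at 12/12 responders on day 28 (1.1.5.2). The inference is not supported.
- **Enhanced disease.** Worsened COVID-19 would present with symptoms. If it led to hospitalisation it would be a serious adverse event, and those are counted to the final visit. Section 1.2.1 sets no day-56 limit on symptom-driven PCR. Missing asymptomatic infection therefore does not defeat that mitigation.

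None of this removes the contradiction between 6.2.8 and 9.1.4 or the mismatch of windows.

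**Conclusion.** The point holds for the SARS-CoV-2 component of AESI incidence, which is descriptive. It may be too high by 2.8 points for each volunteer whose second swab is missed. It may be too low because protocol-ordered PCR reaches only symptomatic cases in about 31% of the endpoint window. Those two sizes follow from the documents alone, taking six months as about 183 days. The 15–24% capture figure rests on outside assumptions (constant incidence, 20–50% asymptomatic) and covers only the symptom-triggered route, so it should not be quoted as the trial's detection rate.

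The decision rule of no vaccine-associated serious adverse event in 33 volunteers (8.2) is untouched, and any-AESI incidence is dominated by granuloma. The point is still worth acting on: the component is in the primary endpoint and goes to the safety board, and the serum needed to improve it is already drawn.

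**What to change.** Reconcile 2.1.1, 6.2.6, 6.2.8, 9.1.4, 9.2 and Table 1, and tabulate three categories separately:

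1. **PCR-confirmed** cases, with or without symptoms, stating whether an outside PCR counts.
2. **Unconfirmed** cases: one negative swab and no second test. These can still be notified promptly but should not be counted as proven.
3. **Serology-only** infection: negative at V1 and positive at a later visit on the planned commercial assay.

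State the observation window for each. Unless the windows are aligned, report protocol-triggered PCR incidence to day 56 and serology-based infection to V7. Say whether adverse events are collected at V6-7, since Table 1, 6.2.6 and 9.2 disagree. Section 6.3.2 should also say at which visits the commercial assay is run, because category 3 needs V1 and the later visits.

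The cost is wording, one derived variable and a small change in the reported rate. If the commercial assay was not meant for every visit, some further assays on serum already drawn would be needed. Extra swabs arise only if the sponsor aligns the windows by extending the trigger.

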6.3. Assessment of Efficacy

6.3.1. Efficacy Parameters

Immunological Efficacy:

Induction of SARS-CoV-2-specific CD8 $^{+}$ and CD4 $^{+}$ T cells is evaluated using:

- IFN- γ ELISPOT
- Intracellular cytokine staining for TNF and IFN- γ

Induction of SARS-CoV-2 specific antibodies:

- ELISA

6.3.2. Methods and Timing for Assessing, Recording, and Analysing of Efficacy Parameters

Immunological Efficacy:

Protocol		
Protocol code and Short Title:	P-pVAC-SARS-CoV-2	Date/Version:08.03.2021/V1.4

Serial measurements of immunological efficacy will be performed prior to peptide vaccination (V1), and V2, V3, V4, at the end of study visit and the follow up visits as outlined in table 1. All scheduled visits have a \pm 1 day window unless otherwise stated. 75ml peripheral blood (60 ml Na⁺-heparin and 15 ml serum) for immunological assays will be obtained prior to vaccination as indicated in table 1. Immunological assays will be performed in the Department of Immunology or the Immunopathological Laboratory, Department of Internal Medicine, University Hospital Tuebingen based on standard SOPs.

Amplification of SARS-CoV-2-specific T cells:

PBMCs from volunteers are pulsed the respective peptide and cultured for 12 days adding IL-2 on days 3, 5, and 7. Peptide stimulated PBMCs are analyzed by enzyme-linked immunospot (ELISPOT) assay on day 12 or by flow cytometry-based tetramer and intracellular cytokine staining as described below.

IFN- γ ELISPOT assay

IFN- γ ELISPOT assays are carried out as described previously.¹¹⁴ In brief, 96-well nitrocellulose plates are coated with anti-IFN- γ . Plates are blocked and PBMCs (ex vivo or after T-cell amplification as described above) are distributed to the wells and re-stimulated with HLA class II peptides. Cytokine staining is performed after incubation period. Analysis is performed according to manufacturer's instructions. Spots are counted using an Immunospot analyzer (according to the cancer immunoguiding program (CIP) guidelines).¹¹⁵

To differ between vaccine induced and natural T-cell induction by SARS-CoV-2 infection we will include, beside the T-cell epitopes included in the CoVac-1 vaccine, additional SARS-CoV-2 T-cell epitopes defined in our preclinical work in the peptide readout⁷⁶.

Cellular conversion rate (CCR) is calculated by dividing the number of volunteers with an immune response by the number of tested participants to a time point (Visit 2, 3, 4 and 5). A volunteer is considered as having developed an immune response due to immunization if ex vivo IFN- γ ELISPOT assay is positive (as described above) and the spot count is at least 2-fold higher than the baseline assay (Visit 1).

Intracellular IFN- γ and TNF staining

The frequency and functionality of peptide-specific CD8⁺ T cells is analyzed by intracellular IFN- γ or TNF staining as described previously.^{114 116} PBMCs are pulsed with individual peptide and incubated in the presence of Brefeldin A and GolgiStop. Cells are labeled using

Protocol		
Protocol code and Short Title:	P-pVAC-SARS-CoV-2	Date/Version:08.03.2021/V1.4

Cytofix/Cytoperm, CD8, CD4, TNF and IFN- γ coupled to fluorochromes. Samples are evaluated on a FACS analyzer.

Enzyme-linked immunosorbent assay (ELISA)

To identify SARS-CoV-2 antibody responses induced by the vaccine, ELISA assays will be performed using serum samples (15 ml serum tube) obtained at the time points described in Table 1. Specific antibodies against the seven SARS-CoV-2 T-cell epitopes will be assessed by ELISA assay at the Department of Immunology, Tübingen. To differ between vaccine induced antibody response additional standard Elecsys® Anti-SARS-CoV-2 assay supplied by F. Hoffmann-La Roche AG, Basel, Switzerland or ADVIA Centaur SARS-CoV-2 Total (COV2T) (Siemens Healthcare Diagnostics GmbH) will be performed at central laboratory of the University Hospital Tuebingen.

Occurrence or relevant (≥ 2 -fold) increase of SARS-CoV-2 specific IgG antibodies compared to baseline are considered as positive.

In the unlikely event of antibody induction by the CoVaC-1 vaccine, neutralization capacity of antibodies will be assessed by SARS-CoV-2 Pseudovirus Neutralization Assay (CD, Creative Diagnostics®)

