The main (per definition) adverse event identified for CoVac-1 is the induction of a granuloma locally at injection site (max. grade 2 in 33% of subjects). These totally asymptomatic granulomas were still detectable on day 28 (time of interim safety analysis). However, it should be noted that granuloma development represents an expected and, even more, intended local reaction after vaccination that is required to enable the continuous local priming of SARS-CoV-2 specific T cells and thus the induction of long-lasting T cell responses while at the same time preventing systemic inflammation. Granuloma formation was also rarely reported after mRNA-based vaccines⁹⁷, where it required systemic steroid treatment. CoVac-1 induced granulomas, in contrast, did not require any investigator-initiated medication and did not affect the daily life activities, in particular the working ability, of our study subjects.

Protocol		
Protocol code and Short Title:	P-pVAC-SARS-CoV-2	Date/Version:08.03.2021/V1.4

Conclusion

Together, in our view the available safety and immunogenicity data of CoVac-1 provide a profound rationale for the continued evaluation of CoVac-1 and thus conduct of the second part of the study. This is based, among others, on the comparison to the three vaccine candidates already approved by the EMA, which showed a clear superiority of CoVac-1 to induce SARS-CoV-2 specific T cell immunity, in terms of frequency, intensity and diversity of T cell responses. Thus, especially in the light of emerging mutations and concerns regarding long-term humoral immunity, CoVac-1 represents a highly promising vaccine candidate to combat COVID-19.

The interim safety and immunogenicity data were presented to the DSMB and all DSMB members agreed with and support the conduct of the second study part.

1.4. Data and Safety Monitoring Board (DSMB):

An independent Data and Safety Monitoring Board (DSMB) will be assembled. The DSMB will be composed of independent experts in the field of immunology and infectiology assessing the progress, safety data and critical efficacy endpoints. The mission of the DSMB is to ensure the ethical conduct of the trial and to protect the safety interests of participants in this trial.

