4.1.2. Exclusion Criteria

Subjects presenting with any of the following criteria will not be included in the trial:

1. Pregnant or lactating females.
2. Participation in any clinical study with intake of any investigational drug interfering with the study primary endpoint
3. Any concomitant disease affecting the effect of the therapeutic vaccine or interfering with the study primary endpoint
4. Any immunosuppressive treatment except low dose corticosteroids ($\leq 10\text{mg}$ prednisolone/day)
5. Prior or current infection with SARS-CoV-2 tested serologically or by throat/nose swab (PCR)
6. History of Guillain-Barré Syndrome
7. Positive serological HIV, hepatitis B or C test. In case of positive HBsAg, volunteer must provide prove of hepatitis B vaccination, otherwise volunteer must be excluded.
8. History of relevant CNS pathology or current relevant CNS pathology (e.g. seizure, paresis, aphasia, cerebrovascular ischemia/hemorrhage, severe brain injuries, dementia, Parkinson's disease, cerebellar disease, organic brain syndrome, psychosis, coordination or movement disorder, excluding febrile seizures as child)
9. Baseline laboratory with lymphocyte count $\leq 1000/\mu\text{l}$
10. Only Part I:
 - o Acute or chronic, clinically significant psychiatric, hematologic, pulmonary, cardiovascular, or hepatic or renal functional abnormality as determined by the

Protocol		
Protocol code and Short Title:	P-pVAC-SARS-CoV-2	Date/Version:08.03.2021/V1.4

Investigator based on medical history, physical exam, and/or laboratory screening test

11. All parts of the clinical trial

- Diabetes mellitus Typ II requiring drug treatment
- Chronic lung disease requiring drug treatment
- Any chronic liver disease or unknown liver abnormalities defined as:
 - ALT and AST $\leq 2.5 \times$ ULN
 - γ -GT $\leq 2.5 \times$ ULN
- Chronic renal failure defined as GFR $< 60 \text{ ml/min}/1,73\text{m}^2$
- Serious pre-existing cardiovascular disease such as NYHA $\geq I$, coronary heart disease requiring coronary surgery or known pAVK \geq grade 2
- Sickle cell anemia
- Obesity (as defined by age adjusted body mass index)

12. Hospitalization at study inclusion

13. Administration of immunoglobulins and/or any blood products within 120 days preceding study entry or planned administration during the study period

14. History of blood donation within 30 days of enrolment or planned donations within the study period

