The investigator will review all information obtained from the screening procedures via an eligibility form. The investigator will confirm, in writing, whether the subject fulfils all criteria for eligibility. Volunteers who fulfil all the inclusion criteria and none of the exclusion criteria will be eligible to participate in the trial. Screening failures, i.e. screened volunteers not in compliance with all criteria, are to be excluded and the reason will be recorded in the volunteer records. Information of volunteer's trial participation can be provided to the volunteer's general practitioner if the volunteer agrees.

6.1.3. *Enrolment*

A volunteer is considered for screening when he or she has signed the Informed Consent form.

In case of confirmation of volunteer's eligibility (volunteers must meet all inclusion criteria and must not meet any exclusion criteria), volunteer will be registered under a specific Vol. ID on a subjects log kept at the trial site. Only these volunteers are enrolled in the study, all others are assessed as screening failures.

The study is open-label.

6.1.4. *Randomisation*

No randomisation will be done in this clinical trial.

6.1.5. *Concomitant Medication and Treatments*

Relevant additional medications and treatments administered to the subjects on entry to the trial or at any time during the trial are regarded as concomitant medications and treatments and must be documented on the appropriate pages of the CRF.

6.1.6. *Permitted Prior and Concomitant Medications and Treatments*

The following concomitant medications and treatments are permitted during the trial.

Part I: No concomitant medication, apart from contraception for FCBP.

Part II : Any concomitant medication (already applied at screening) for e.g. other diseases are allowed except for medications stated in section 6.1.7.

6.1.7. *Prohibited Prior and Concomitant Medications and Treatments*

The following concomitant medications and treatments are prohibited during the trial:

Protocol		
Protocol code and Short Title:	P-pVAC-SARS-CoV-2	Date/Version:08.03.2021/V1.4

- Immunosuppressive agents apart from (≤ 10 mg prednisolone or equivalent)
- During the trial, other vaccinations or non-urgent medical interventions are prohibited. Initiation of new medications, regardless of indication must be discussed with the investigator and must be noted on the participant's record.

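### The T-cell responder rule ignores the infection data the trial collects, and V1.4 does not exclude prior SARS-CoV-2 vaccination; the likely effect on the conversion rate is modest

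*Supplement*

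**What the plan says.** All references are to protocol V1.4 (08.03.2021). No separate analysis plan is among the documents.

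**Responder rule.** Section 6.3.2 reads: "A volunteer is considered as having developed an immune response due to immunization if ex vivo" IFN-γ ELISPOT is positive and the spot count has at least doubled against Visit 1. The CCR is then obtained "by dividing the number of volunteers with an immune response by the number of tested participants to a time point", at Visits 2, 3, 4 and 5. Section 2.2.1 asks for a response to one or more of the vaccine epitopes, so one of six is enough. Section 8.3 takes the proportion with a T-cell response within 56 days as the secondary efficacy endpoint and refers back to section 6.3.1 for its assessment.

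**Data that bear on infection.** Immediately before the CCR definition, section 6.3.2 states: "To differ between vaccine induced and natural T-cell induction by SARS-CoV-2 infection we will include, beside the T-cell epitopes included in the CoVac-1 vaccine", further epitopes from the preclinical work. The ELISA paragraph adds a commercial antibody assay. Section 6.2.8 provides for PCR when typical symptoms occur up to day 56, and a positive result is recorded as an AESI.

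**Other vaccines.** Exclusion no. 5 in section 4.1.2 names prior or current infection only; neither that list nor the synopsis mentions an earlier SARS-CoV-2 vaccine. Section 6.1.7 says: "During the trial, other vaccinations or non-urgent medical interventions are prohibited". Yet section 1.3 rests part of its case on a "comparison to the three vaccine candidates already approved by the EMA".

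**The concern.** The rule assigns a cause, immunization, while leaving out the measurements the protocol says it takes in order to tell vaccination from infection. The vaccine peptides were chosen because convalescents recognise them (sections 1 and 1.1.4), so infection can plausibly produce the same positive assay. Symptom-triggered PCR, with a fever threshold above 39 °C, will miss mild or silent cases. Those would show only in the serology and the non-vaccine epitopes, which the rule does not consult.

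The eligibility gap is separate. In March 2021 the protocol itself discusses three approved vaccines and is opening Part II to ages 56-80. A volunteer vaccinated days before Visit 1 breaches no written criterion unless the screening serology happens to detect that vaccine's antibody, and the documents do not say which antigen that test measures. Such a dose could also bring its own reactions into the 28-day solicited window; section 1.1.5.3 cites chills in 32% to 50% of recipients of the approved vaccines.

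At stake is the interpretation of the secondary immunogenicity endpoint, and of the exploratory 3- and 6-month persistence results. The sponsor uses the interim T-cell results to argue for continuing (section 1.3).

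**Working it through.** **1. The plan's own figures.** The only design calculation is for the serious-adverse-event test in section 8.1.1. With 33 evaluable volunteers and at least one event required, power at 5% is 1 − 0.95^33 = 0.816 (stated 81.6%) and the actual level is 1 − 0.9999^33 = 0.0033 (stated 0.003). Both reproduce, and neither concerns the CCR. No target, power or precision is given for the CCR, so the check is of the definition and of its sensitivity.

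**2. What is collected against what is used.**
- Non-vaccine epitopes (6.3.2): collected; not in the responder rule, the CCR formula or 8.3.
- Commercial antibody assay (6.3.2): collected; not in any of the three.
- PCR on symptoms to day 56 (6.2.8): collected; goes to AESI reporting only.
- Vaccination on study (6.2.8): noted at unscheduled visits; no consequence for the analysis is stated.

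**3. Weight of one volunteer.** Part II: 1/24 = 4.2 percentage points. Both parts: 1/36 = 2.8 points.

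**4. Expected inflation.** Only a volunteer who would not have responded to CoVac-1 can be misattributed. If infection strikes with probability q by the visit, independently of vaccine response, and always satisfies the rule, then

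counted rate = CCR + (1 − CCR) × q, so inflation = (1 − CCR) × q.

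Inputs: Part I showed 12/12 responders at day 28 (section 1.1.5.2). The one-sided 95% lower bound is 0.05^(1/12) = 0.779, taken as 78%. The documents give no infection risk, so q is assumed.

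| Assumed true CCR | q = 2% | q = 5% | q = 10% |
|---|---|---|---|
| 50% | 1.0 | 2.5 | 5.0 |
| 78% | 0.4 | 1.1 | 2.2 |
| 90% | 0.2 | 0.5 | 1.0 |
| 100% | 0 | 0 | 0 |

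Entries are percentage points. At 78% and q = 10%, the expected number misattributed in Part II is 24 × 0.22 × 0.10 = 0.5 volunteers.

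**5. Will the situation arise?** The chance of at least one infected volunteer among 24 is 1 − (1 − q)^24: 38%, 71% and 92% at q = 2%, 5% and 10%. A handling rule is therefore quite likely to be needed, even though the average shift is small.

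**6. Prior vaccination.** The comparison is with a pre-dose baseline. An established response to an earlier vaccine is already in the Visit 1 count and makes a doubling harder, which lowers the CCR. Only a response still rising after Visit 1 pushes upward. By the protocol's account the approved vaccines act on spike alone (section 1.1.5.3), and Table 3 labels one of the six peptides as spike. One peptide is enough under section 2.2.1, so the route is narrow but open.

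**The case against.** Much of the case on the other side stands.

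- **The rule is not a bare doubling.** A reader might infer that any 2-fold rise is credited. It is not: a positive assay is also required. In V1.4, however, the text to which that condition refers back gives a guideline reference and no numerical cut-off.
- **The purpose is stated.** The epitope readout is described in the same section, and tables with and without affected volunteers are commonly left to an analysis plan. That is fair for the tables. But the protocol itself fixes the responder definition and its causal label, and eligibility belongs in the protocol.
- **Prior vaccination does not simply inflate the CCR.** That inference fails for the reasons in step 6 of the working. Vaccines given on study are prohibited by section 6.1.7. What remains is a dose shortly before Visit 1, or a breach for which no handling is written.
- **Not every infected volunteer inflates the rate.** With conversion near 100%, almost none would. Nor would infection shortly before a visit necessarily register, since section 1.1.1 says T-cell expansion in natural infection takes several days.
- **Reactions would not automatically be charged to CoVac-1.** Section 9.3.2 has the investigator weigh alternative causes, and section 6.1.5 requires relevant medications and treatments at entry to be documented. A recent dose would complicate that assessment, not predetermine it.
- **Dropping post-infection samples from the main analysis would be debatable.** Section 3 states an intention-to-treat analysis, exclusion after a post-baseline event could discard genuine responders, and section 1 describes cross-reactive epitopes in unexposed people. This shapes the remedy.

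**Conclusion.** Two gaps stand. As written, sections 6.3.2 and 8.3 can count a true non-responder infected after Visit 1 as a CoVac-1 responder although the data to recognise the case are collected. And V1.4 says nothing about prior receipt of a SARS-CoV-2 vaccine at entry.

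The size is modest: 4.2 points per misattributed non-responder in Part II, and an expected inflation of at most about 2.2 points for q up to 10% and a true CCR of 78% or more. This rests on an assumed q, on independence of infection and vaccine response, and on infection always meeting the rule. The 78% comes from volunteers aged 18-55, and section 1.1.5.2 does not say whether the 12/12 is the ex vivo result that the CCR uses. Section 1.1.1 notes fewer CD4+ T cells in older people, so a lower rate in Part II is possible; the 50% row shows the effect.

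A reader might conclude that the conversion rate is materially biased upward or that a decision hangs on it. The documents do not support that: the analysis is descriptive with no confirmatory test. Persistence at 3 and 6 months is exploratory and lies outside the Visit 2-5 rule, but it has the same lack of a handling rule, and the PCR trigger ends at day 56. The change is worth making because attribution is the point of the label and the remedy is cheap.

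**What to change.** In sections 6.3.2 and 8.3, keep the CCR over all tested volunteers. Add that a response is not labelled vaccine-induced if it is first seen at or after any of these: a positive SARS-CoV-2 PCR, seroconversion on the standard assay, a new response to the non-vaccine epitopes compared with Visit 1, or receipt of another SARS-CoV-2 vaccine. Report the CCR and the 3- and 6-month persistence with and without these volunteers. The Visit 1 comparison guards against counting pre-existing cross-reactivity as infection.

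In section 4.1.2, exclusion no. 5, and in the synopsis, add previous receipt of any SARS-CoV-2 vaccine.

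The cost is a few lines of text, one extra table and perhaps a few screening failures. No new assay is needed.
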